5.6.3. Statistical models

5.6.3.1. Cox proportional hazards model

Cox model will be computed using the SAS PHREG procedure. The dependent variable is the time between first day of gestation and the event or at censoring.

For the spontaneous abortion analysis, time to event for subject with no spontaneous abortion will be censored at the earliest of the following time-points:

- 161 days (end of week 23) or 133 days (end of week 19)
- Lost-to-follow up (*de*-enrolment from CPRD *GOLD*) (**Amended 14 March 2013**)
- Mother's death
- Pregnancy termination

The main model (Model 1) will include the exposure status (exposed vs. non-exposed) as a binary independent variable and the age at first day of gestation as a continuous covariate. The adjusted HR will be derived as the exponential of the coefficient associated with the exposure status and its 95% Wald CI.

Survival curve will be depicted for the exposed and non-exposed cohort (using the Option Plots(overlay)=survival in the SAS PHREG procedure).

The following models will also be computed as sensitivity analyses:

Model 2: A Cox model including, in addition to the age at first day of gestation, other covariates

- Smoking during pregnancy (3 classes: yes, no, unknown)
- Exposure to H1N1 pandemic (yes, no)
- Region (class variable)
- Alcohol consumption during pregnancy (3 classes: yes, no, unknown)
- Diabetes during pregnancy (3 classes: yes, no, unknown)

- High blood pressure during pregnancy (3 classes: yes, no, unknown)
- Number of previous pregnancies (sum of the number of previous births and the number of previous abortions)
- Vaccination with another vaccine within 90 days before first day of gestation or within the 90 days after first day of gestation (binary variable)
- Use of contra-indicated drugs during the first trimester of pregnancy (three classes: non contraindicated drug, manufacturer advice “to-use with caution” drugs, manufacturer mentioned advice “to-avoid” drugs)

Covariates occurring in less than 5% of the subjects (percentage will be computed over both exposed and non-exposed cohorts) will not be included in the model.

Model 3: A Cox model will compare the exposed cohort according to the number of *Cervarix* doses (3 classes: 1 dose, 2 doses, 3 doses) vs. the non-exposed cohort, using the same model as for the primary analysis (model 1). In this model, the exposed women with more than 3 doses of *Cervarix* will not be included.

Model 4: A Cox model identical to Model 1 will be performed for any abortion occurring before week 24 of gestation. Any abortion will include spontaneous abortion, therapeutic/induced abortion and other abortion.

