4.2.2.1. Inclusion criteria for exposed cohort

All subjects must satisfy all of the following criteria at entry into the exposed cohort:

- Full date (day/month/year) of first day of LMP available in the database or calculated from Estimated date of delivery (EDD) (day/month/year)
- Female, aged between, and including, 15 and 25 years of age at LMP
- Recorded in the CPRD *GOLD* for at least 12 months at LMP

- First day of LMP available in the database or calculated from EDD (day/month/year) between September 1st 2008 and June 30th 2011
- At least one dose of *Cervarix* received between September 1st, 2008 and June 30th, 2011
- Full date (day/month/year) of *Cervarix* vaccination(s) available
- First day of LMP available in the database or calculated from EDD between 30 days before and 90 days after any dose of *Cervarix*
- Subject defined as acceptable in CPRD **GOLD**¹

(Amended 14 March 2013)

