5.4. Sample size calculation

Using a two-sided log-rank test with type I error rate of 5% (Software: PASS 2005) and results from the feasibility analysis which has estimated the potential eligible subjects (see section 3.2), the study would have the following power to detect a relative risk (Hazard ratio, HR) of 2.0 of spontaneous abortion between the exposed and non-exposed subjects: 98% power if the first day of LMP is between 30 days before and 45 days after and 99% power if the first day of LMP is between 30 days before and 90 days after any dose of *Cervarix*. The HR detectable with 80% power would be 1.69 and 1.60, respectively.

Those calculations are based on the following assumptions:

- Rate of spontaneous abortion: approximately 11.5% of pregnancies (see section 3.2, feasibility analysis).
- Proportion of dropped out subjects before the first 23 weeks of gestation: 20%.

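### Model 2 enters covariates measured after time zero as fixed, and Model 3 has no stated dose-counting date, so an early loss can distort both sensitivity analyses

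*Combined protocol and SAP*

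**What the plan says.** In section 5.6.3.1, time runs from the first day of gestation to the event or censoring. Model 1, the primary model, contains exposure and age only. Models 2 and 3 are labelled sensitivity analyses.

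Model 2 adds, among others:
- smoking, listed as "Smoking during pregnancy (3 classes: yes, no, unknown", with alcohol, diabetes and high blood pressure defined in the same way;
- "Use of contra-indicated drugs during the first trimester of pregnancy", in three classes;
- another vaccine in the 90 days before "or within the 90 days after first day of gestation (binary variable";
- region, number of previous pregnancies and H1N1 period.

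Covariates present in under 5% of women are left out. None is described as time-dependent. Section 5.2.4.1 lists lifestyle and medical conditions for the pregnancy period and classifies drugs used in the first trimester. Section 5.6.1 rules out substitution of missing data.

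Model 3 divides the exposed cohort by number of Cervarix doses ("3 classes: 1 dose, 2 doses, 3 doses) vs. the non-exposed cohort") and omits exposed women with more than three. The protocol body gives no date to which doses are counted. Section 4.1 rules out a further dose before the outcome, but only for the non-exposed cohort. Variable algorithms are placed in Appendix A, whose content is not in the text available for this review.

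**The concern.** A fixed covariate in a Cox model should be known at time zero. A woman who loses the pregnancy at week 7 has had little time to be asked about smoking, diagnosed or prescribed a drug. For her, 'unknown' or 'no' is partly a consequence of the endpoint, and adjusting for it removes some of the effect under study.

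Model 3 has a related problem. Section 1.2 states that Cervarix is not recommended in pregnancy, so a remaining dose may be deferred while the pregnancy continues and resumed after a loss. Without a counting date, the dose class can reflect the outcome.

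Model 2 is the only planned model that adjusts the spontaneous abortion comparison for anything beyond age, and Model 3 is the only dose analysis. If either disagrees with Model 1, a reader could not separate confounding or dose response from artefact. In a safety study, attenuation of a raised HR errs in the unfavourable direction.

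**Working it through.** **1. The plan's own figure.** Section 5.4 gives "98% power if the first day of LMP is between 30 days before and 45 days after" for HR 2.0, from a two-sided 5% log-rank test. Inputs are 243 exposed and 667 non-exposed (section 3.2) and a risk of 11.5% (section 5.4). With Freedman's formula:
- Exposed risk: 1 − 0.885² = 0.2168.
- Events: D = 243 × 0.2168 + 667 × 0.115 = 52.7 + 76.7 = 129.4.
- Allocation ratio: φ = 243/667 = 0.364.
- z = √(129.4 × 0.364) × (2 − 1)/(1 + 2 × 0.364) − 1.96 = 2.01, so power is 97.8%.

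The wider window (379 exposed) gives 99.4% against 99% stated. The HRs detectable with 80% power are 1.68 and 1.59 against 1.69 and 1.60 stated. These figures take no dropout. With the 20% dropout as a competing exponential, power is 96.5% and 98.8%; removing 20% of all events gives 94.4% and 97.8%. The power statement is not in dispute; it fixes the scale of the study.

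**2. What is known at time zero.**

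| Covariate | Known at first day of gestation? |
|---|---|
| Age, region, previous pregnancies | Yes |
| H1N1 period (by LMP date, section 5.6.2) | Yes |
| Smoking, alcohol | No; the recording period can be cut short by a loss |
| Diabetes, high blood pressure | No; may drop out under the 5% rule |
| First-trimester drugs | No |
| Other vaccine, −90 to +90 days | Partly; the window is not cut short by a loss |

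**3. Model 2 simulation.** Cohorts were in the ratio 243:667, scaled up 300-fold, with 8 replicates. The following assumptions are not in the documents:
- 80% of the loss hazard falls on days 36–91 and the rest by day 161; 20% of women are censored.
- Smoking is recorded at a visit on days 56–84 if the woman is still pregnant, otherwise with the probability shown below.
- Drug use is 30% over 91 days.
- Neither smoking nor drugs has a true effect.

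| Recording probability, exposed / non-exposed | True HR 1.0 | True HR 1.5 | True HR 2.0 |
|---|---|---|---|
| 0.3 / 0.3 | 1.00 | 1.38 | 1.71 |
| 0.7 / 0.7 | 1.00 | 1.45 | 1.88 |
| 0.9 / 0.9 | 1.00 | 1.48 | 1.96 |
| 0.9 / 0.7 | 1.11 | 1.65 | 2.14 |
| 0.7 / 0.9 | 0.90 | 1.33 | 1.76 |

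The 'unknown' class acquires an HR of about 15 to 51, and the inert drug an HR of about 0.73 to 0.82. The shift in the exposure HR comes from the 'unknown' class. In a separate single run with true HR 2.0, Model 1 gave 2.05; adding the drug alone left it at 2.05, and adding smoking alone gave 1.77. With smoking known for every woman at time zero and no drug term, the exposure HR returns to 1.00, 1.50 and 2.00.

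**4. Model 3 simulation, true HR 1 in every class.** There were 60,000 exposed and 120,000 non-exposed women. Uptake was 62.2%, 54.2% and 31.8% (section 3.1), with spacing of 0, 1 and 6 months (from the title of the clinical report in section 9). Assumptions: pregnancy is recognised at day 42; doses falling due in pregnancy are deferred with the probability shown; deferred doses are resumed with probability 0.8 after a loss and 0.3 after a continuing pregnancy.

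| Doses counted | Deferral | HR for 1 / 2 / 3 doses |
|---|---|---|
| Ever | 0 | 0.96 / 1.00 / 0.96 |
| Ever | 0.5 | 0.77 / 0.71 / 1.29 |
| Ever | 0.9 | 0.56 / 0.57 / 1.73 |
| To end of follow-up | 0 | 1.61 / 1.13 / 0.63 |
| To end of follow-up | 0.5 | 1.21 / 1.08 / 0.79 |
| To end of follow-up | 0.9 | 1.06 / 1.02 / 0.96 |
| To LMP + 30 days | 0, 0.5 or 0.9 | all between 0.98 and 1.03 |

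**The case against.** Both models are sensitivity analyses. No decision rule depends on them, the plan has no dose-response objective, and the primary HR comes from Model 1. Confounding is also addressed by having vaccinated women in both cohorts, by age adjustment and by baseline comparisons. All of this stands and limits the consequence.

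The bias sizes depend on assumed recording and deferral rates. The Model 2 attenuation is also modest against sampling error. At HR 1 there would be about 243 × 0.115 = 28 and 667 × 0.115 = 77 events, so the 95% interval spans a factor of exp(1.96 × √(1/28 + 1/77)) = 1.54 each way before dropout. A fall from 2.0 to 1.71 is a factor of 1.17. This stands too, but the bias is systematic and avoidable.

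A reader might infer that every Model 2 covariate is contaminated. The table in step 2 shows otherwise. In particular, the other-vaccine window is a calendar window: a woman with a week-7 loss can still be vaccinated and counted to day 90. Its part after LMP is nevertheless measured after time zero.

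A reader might also say that Model 3 adjusts for a consequence of the outcome. It does not; dose count is its exposure classification. Some women qualify on their third dose and have none left to defer. Appendix A may contain a counting rule, so its absence is shown only for the protocol body.

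**Conclusion.** The point holds as a weakness of the two sensitivity analyses. In Model 2, smoking, alcohol, diabetes, high blood pressure and first-trimester drugs are ascertained after time zero but entered as fixed, so an early loss can influence them. A raised exposure HR can then be attenuated (illustratively 2.0 to about 1.7–1.96), or shifted either way if recording differs between cohorts. In Model 3, the dose class can depend on whether the pregnancy continued, and a spurious dose trend can appear in either direction. Model 3 is close to unbiased if doses are counted to a fixed early date, or if later doses do not depend on the pregnancy and all are counted.

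Three stronger readings are not supported. The loss does not by itself determine the covariate; it can influence it. Model 2 does not create a false signal as such: with equal recording and a true HR of 1 it is unbiased for exposure, and the documents give no evidence that recording differs by cohort. The primary result is not biased by this point, because Model 1 uses none of these variables.

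All sizes rest on the assumptions listed in the working and are illustrations, not forecasts.

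**What to change.** In section 5.6.3.1, derive the Model 2 covariates from records at or before the first day of gestation: last recorded smoking and alcohol status, pre-existing diabetes and hypertension, and drugs and other vaccines in the preceding 90 days. Enter any later drug or vaccine exposure only as a time-dependent covariate. Look-back exists, because women in both cohorts must have been in the database at least 12 months by LMP (section 4.2.2.1: "for at least 12 months at LMP"; section 4.2.2.2 likewise).

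For Model 3, count doses to one fixed date for all exposed women, such as LMP + 30 days. Under section 4.2.2.1, LMP can be at most 30 days before a qualifying dose, so this is the latest date on which a dose can qualify. Counting doses before the outcome would not do, since that limit itself depends on the outcome. Counting to the qualifying dose is ambiguous when a woman has two. If Appendix A already fixes a date, state it in the body.

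Cost: section 5.2.4.1 lists lifestyle, condition and drug data for the gestation period only, so a further extraction of earlier records is needed; the database is held in-house. Smoking and alcohol status may be older, and some 'unknown' values will remain, because 12 months in the database does not guarantee a record.

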Based on the recent CPRD **GOLD** release (2012Q3), 2440 subjects out of 78,111 subjects (3.1%) 15-25 years of age and exposed to *Cervarix* were identified with a simultaneous *Cervarix* vaccination and a LMP date between September 1st 2008 and June 30th 2011. Among these potential eligible subjects (not taking into account all inclusion/exclusion criteria as defined below in this protocol), 243 were identified as being exposed to *Cervarix* vaccine (first day of LMP between 30 days before and 45 days after any dose), 379 (first day of LMP between 30 days before and 90 days after any dose) and 667 as non-exposed (first day of LMP between 120 days and 18 months after the last dose of *Cervarix* vaccine).

The estimate for spontaneous abortions in the CPRD **GOLD** of 11.6% is in line with earlier literature reports in US and UK [e.g. 13.8%, Saraiya, 1999; 7.0%, Seamark, 2001; 14.0%, Ventura, 2008; 11.5% and 10.2%, Wacholder, 2010; 14.9%, Devine, 2010].

Based on the numbers obtained above, the proposed study could be performed using CPRD **GOLD** data source. The risk of spontaneous abortions in the exposed cohort will be compared to that in the non-exposed cohort.

(Amended 14 March 2013)

[figure not shown]

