4.2.2.2. Inclusion criteria for non-exposed cohort

All subjects must satisfy all of the following criteria at entry into the non-exposed cohort:

- Full date (day/month/year) of first day of LMP available in the database or calculated from EDD (day/month/year)
- Female, aged between, and including, 15 and 25 years of age at LMP
- Recorded in the CPRD **GOLD** since at least 12 months at LMP
- First day of LMP available in the database or calculated from EDD (day/month/year) between September 1st 2008 and June 30th 2011
- At least one dose of *Cervarix* received between September 1st 2008 and June 30th 2011
- Full date (day/month/year) of *Cervarix* vaccination(s) available
- First day of LMP available in the database or calculated from EDD between 120 days and 18 months after the last dose of *Cervarix*
- Subject defined as acceptable in CPRD **GOLD**

(Amended 14 March 2013)

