5.5.3. Pregnancy outcomes

5.5.3.1. Endpoints related to spontaneous abortion

Proportion of spontaneous abortion will be calculated for the exposed and the non-exposed cohorts as the number of pregnant women with spontaneous abortion divided by the total number of included pregnant women.

The risk of abortion according to gestational time will be depicted using Kaplan-Meier curves.

The primary analysis will be the comparison of the risk of spontaneous abortion during the first 23 weeks of gestation and during the first 19 weeks of gestation in the exposed cohort and the non-exposed cohort using a Cox regression model with spontaneous abortion as the dependent variable, a dichotomous exposure as the independent variable and with age at first day of gestation as a covariate. The HR and its 95% confidence interval (CI) will be derived. The analysis will be done for two risk periods for the exposed subjects: the 30 days before to 45 days after any dose of *Cervarix* period and the 30 days before to 90 days after any dose of *Cervarix* period. The main analysis (primary objective) is the -30 to +45 day risk period.

For subjects with no spontaneous abortion, time-to-event will be censored at: the end of week 23 (or week 19), date of induced or therapeutic abortion, date of death, date of last available pregnancy data whichever occurs first.

The following sensitivity analyses will be performed:

- Cox regression including in addition to the age at the first day of gestation other covariates (region, smoking, alcohol consumption, vaccination, diabetes, high blood pressure, number of previous pregnancies, other vaccination, use of contra-indicated drugs, exposure to H1N1 pandemic)
- Analysis of all abortions (defined as induced, therapeutic and other abortion) using the same model as for the primary analysis

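### The 5% rule for Model 2 covariates pools both cohorts, ignores imbalance between them, and could drop from this sensitivity model a covariate carried by up to 18.5% of exposed women

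*Combined protocol and SAP*

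**What the plan says.** Section 5.6.3.1 sets out the Cox models. The primary one adjusts only for the woman's age when gestation begins: "The main model (Model 1) will include the exposure status (exposed vs. non-exposed) as a binary independent variable and the age". It then states: "The following models will also be computed as sensitivity analyses". Model 2 adds smoking, the H1N1 period, region, alcohol, diabetes, high blood pressure, previous pregnancies, other vaccination and contra-indicated drugs. The rule for leaving one of these out is: "Covariates occurring in less than 5% of the subjects (percentage will be computed over both exposed and non-exposed cohorts) will not be included".

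One listed covariate matters most here: "Vaccination with another vaccine within 90 days before first day of gestation or within the 90 days after first day of gestation (binary variable").

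The cohort sizes come from the feasibility count in section 3.2: "243 were identified as being exposed to *Cervarix* vaccine" in the -30 to +45 day window, and "379 (first day of LMP between 30 days before and 90 days after any dose) and 667 as non-exposed". Section 5.5.3.1 names the main window: "The main analysis (primary objective) is the -30 to +45 day risk period". For the non-exposed cohort, section 4.2.2.2 requires: "First day of LMP available in the database or calculated from EDD between 120 days and 18 months after the last dose of" the vaccine.

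Section 5.6.2 tabulates these factors by cohort. Smoking, alcohol, diabetes, high blood pressure and the H1N1 period also get a Fisher's exact test; other vaccines and contra-indicated drugs are only tabulated.

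**The concern.** Whether omitting a covariate biases the exposure hazard ratio depends on how differently it is distributed between the cohorts and on how strongly it predicts the outcome. A pooled percentage measures neither. Exposed women are 243 of 910 (27%) in the main window, so a factor can be fairly common among them and still look rare overall.

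For other vaccination, the cohort definitions themselves push towards imbalance. An exposed woman's first day of LMP lies between 30 days before and 45 (or 90) days after a dose, so a vaccine given on the same day as that dose always falls within 90 days either side. A non-exposed woman's last dose is at least 120 days before LMP, so a vaccine given with it always falls outside.

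Models 1, 3 and 4 and the logistic models adjust for age only. If Model 2 has lost an unbalanced covariate, no other planned analysis adjusts for it, and no step returns an imbalance seen in the section 5.6.2 tables to the model. Agreement between Models 1 and 2 would then be weaker reassurance than it appears. Because the rule is applied to whichever cohorts are being compared, a covariate near 5% could also be kept in one window and dropped in the other.

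**Working it through.** The plan states no figure of its own on this point. The inputs are the section 3.2 counts (243, 379 and 667) and the 5% rule in section 5.6.3.1. The covariate's effect on spontaneous abortion is not in the documents, so a range of 1.25 to 3 is assumed.

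**1. Largest exposed prevalence that can be dropped.** Take the largest whole number of carriers below 0.05 × (exposed + non-exposed), and suppose all are exposed.

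- -30 to +45 days: 0.05 × (243 + 667) = 45.5, so 45 carriers; 45/243 = 18.5% against 0%, pooled 45/910 = 4.9%.
- -30 to +90 days: 0.05 × (379 + 667) = 52.3, so 52 carriers; 52/379 = 13.7% against 0%.
- With the rounded sizes in Table 1 (240 and 660), 5% of 900 is exactly 45, so 44 carriers can be dropped; 44/240 = 18.3%.

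Any carriers in the non-exposed cohort lower the limit. With 3% there (20 women), at most 45 − 20 = 25 exposed carriers could be dropped, or 25/243 = 10.3%.

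**2. Bias from omission.** With prevalence p1 in exposed and p0 in non-exposed women and covariate relative risk RR, the exposure effect is multiplied by (1 + p1(RR − 1)) / (1 + p0(RR − 1)). At the main-window bound (18.5% against 0%):

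| Assumed RR | Bias factor |
|---|---|
| 1.25 | 1.046 |
| 1.5 | 1.093 |
| 2 | 1.185 |
| 3 | 1.370 |

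At RR 2, 10% against 3% gives 1.10/1.03 = 1.07. If the same 45 carriers were all non-exposed (45/667 = 6.7%), the factor would be 1/1.067 = 0.94; if evenly spread, 1.00.

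**3. Simulation.** Cox models were simulated for 243 against 667 women, 11.5% risk, true exposure hazard ratio 1 and assumed covariate hazard ratio 2. Two settings were used: age plus the covariate only (with 20% drop-out), and about 20 other covariates also in the model.

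| Carriers, exposed against non-exposed | Dropped (two settings) | Kept (two settings) |
|---|---|---|
| 18.5% against 0% | 1.17, 1.18 | 0.99, 1.00 |
| 15% against 1% | 1.12, 1.11 | 1.00, 0.98 |
| 10% against 3% | 1.06, 1.07 | 1.00, 1.00 |

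At the bound in the simpler setting, covariate hazard ratios of 1.5 and 3 gave 1.08 and 1.33 when dropped. The covariate can be fitted even when no non-exposed woman carries it.

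**4. What the rule does not do.** At RR 2, a covariate at 18.5% against 0.15% is 5.06% pooled and is kept, with bias factor 1.183 if it were omitted. One at 50% against 20% is kept, with factor 1.25. The rule is blind to confounding; it does not select for it.

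**The case against.** Three stronger readings are tempting, and the documents support none of them.

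- A reader might infer that the rule discards covariates exactly when they confound most. It does not: step 4 shows that stronger confounders above 5% pooled are kept. The statement holds only among covariates already below the threshold.
- A reader might infer that the design itself produces the 18.5% against 0% pattern for other vaccination. The timing argument covers only vaccines given with the relevant dose. Non-exposed women can receive other vaccines at separate visits within the roughly 180-day window, and the documents give no frequency of co-administration. If more than 18.5% of exposed women carried the covariate, it would pass the threshold and be kept.
- A reader might infer that the primary result is biased by this rule. Model 1 never contains these covariates, so its hazard ratio cannot change.

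The sparsity threshold also has a rationale. Model 2 has about 15 parameters before region. With 910 women at 11.5%, about 105 events are expected, or 84 after 20% drop-out: roughly 6 to 7 per parameter. A per-cohort rule could admit a covariate with only 13 exposed carriers, about 13 × 0.115 = 1.5 expected events and a chance of 0.885^13 = 20% of none. This is a fair reason to have a threshold, but not to compute it pooled: with about 20 other covariates in the simulated model, admitting 13 carriers cost almost nothing.

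The tables in section 5.6.2 would make an imbalance visible, and no section says that agreement between Models 1 and 2 will be read as absence of confounding. Both points stand and lower the importance. They do not put a dropped covariate back into the model; doing so after seeing the tables would be a change from plan to be justified under section 5.7. Nor are the two windows' Model 2 results generally non-comparable: only covariates near 5% could switch, and both windows share the same 667 non-exposed women.

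**Conclusion.** The point holds in a limited form. The pooled rule takes no account of imbalance and could remove from Model 2 a covariate carried by up to 18.5% of exposed women in the main window, or 13.7% in the wider one. Both are upper bounds, reached only if no non-exposed woman is a carrier. They rest on feasibility counts made before all eligibility criteria were applied.

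At an assumed covariate hazard ratio of 2, the Model 2 exposure hazard ratio would be inflated by a factor of about 1.06 to 1.07 under moderate imbalance and 1.17 to 1.18 at the bound. The documents give neither the covariate effects nor their frequencies by cohort, so the actual size is unknown and could be nil. Other vaccination is the most plausible candidate because its direction of imbalance follows from the cohort definitions. The primary analysis is untouched. This is an optional improvement to a sensitivity analysis.

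**What to change.** In section 5.6.3.1, replace the pooled criterion: drop a listed covariate only if it occurs in less than 5% of the exposed cohort and in less than 5% of the non-exposed cohort. Make the decision once, on the -30 to +90 day exposed cohort and the non-exposed cohort, and use the resulting set in Model 2 for both exposure windows. The same sentence could say how 5% is counted for covariates with more than two classes, which the rule leaves open.

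Effect: 5% of 379 is 18.95, so at most 18 exposed carriers could be dropped, or 4.7% in the wider window. If all 18 fell within the narrower window, that would be 18/243 = 7.4%, and the worst exposed-only factor at RR 2 falls from 1.185 to 1.074. Deciding separately on the narrower window would limit it to 12/243 = 4.9% and 1.049, but the two windows could then use different covariate sets.

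Cost: one reworded sentence and a few more sparse parameters in a sensitivity model. In the most extreme simulated case the standard error of the log hazard ratio rose from about 0.24 to 0.27, a confidence interval about one eighth wider on the log scale (0.27/0.24 = 1.125). Where no non-exposed woman carries the covariate, the adjustment rests wholly on the contrast within the exposed cohort, which the report should state.
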